9.3.3 ANALYSIS OF THE SECONDARY ENDPOINTS

Analysis of Disease Severity (Aim 1)

In Aim 1, we will assess a secondary endpoint, vIGA, which is an ordinal scale that provides a global assessment of the patient's AD disease severity. vIGA is scored on a 5-point ordinal scale ranging from 0 (clear) to 4 (severe). We will apply the same general modeling procedure using generalized estimating equations with the ordinal outcome of vIGA. The reference category will be 0 = clear. The equivalence margin for vIGA is 0.5, which is smaller than the minimal clinically important difference and considered a conservative equivalence margin by AD experts.

We will also assess a secondary endpoint of patient-reported symptoms using the validated instrument POEM. For POEM, we will use the same modeling method as the one described for EASI. The scores for the POEM instrument range from 0 to 28. The equivalence margin for POEM is 3.4, which is the minimal clinically important difference defined in the AD literature.²⁸

Analysis of Health-Related Quality of Life and Access-to-Care Measures (Aim 2)

In Aim 2, we will compare health-related quality of life between patients from practices randomized to the two interventions. The hypothesis is that the TCH model results in *equivalent* improvement in health-related quality of life as that in the in-person arm, as measured by DLQI and Children's DLQI (CDLQI), and EQ- 5D-5L/EQ-5D-Y.

DLQI and CDLQI are validated dermatology-specific quality-of-life instruments for adults and children, respectively. The scores range from 0 to 30, with higher scores indicating more severe impact on quality of life. The equivalence margin for DLQI and CDLQI is \pm 4, which corresponds to the established minimal clinically important difference.²⁹

EQ-5D-5L and EQ-5D-Y are valid and reliable, generic preference-based quality of life instruments. In dermatology, EQ-5D-5L has been used in numerous AD trials. The equivalence margins for the utility index (\pm 0.15) and VAS (\pm 10) of the instrument are no larger than half of SD (Cohen's d = 0.5) and are considered the minimal clinically important difference.

The same repeated-measures, equivalency-evaluation approach described above for Aim 1 "Analysis of Atopic Dermatitis Disease Severity" will be used to compare responses to DLQI/CDLQI, and EQ-5D-5L/EQ-5D-Y between patients from practices randomized to the TCH model and in-person care across time.

The hypothesis for access-to-care measures is that TCH provides *superior* access to specialist care than in- person model. For these analyses, access-to-care measures include transportation and time needed for evaluation.

Linear regression models will be used to test whether there is a difference between the groups.

Analysis of Costs (Aim 3)

Cost analysis in healthcare research is essential for evaluating the financial impact of different treatment models on both patients and healthcare systems.²⁶⁻²⁷ For this aim, out-of-pocket (OOP) costs represent a significant factor in determining the feasibility and accessibility of team-based connected health (TCH) compared to traditional in-person care for atopic dermatitis (AD). By analyzing OOP expenditures, this study will provide insights into whether TCH offers a cost-effective alternative while maintaining equivalent clinical outcomes.³¹⁻³⁸

Healthcare utilization will be analyzed using the Cornell Services Index (CSI), which quantifies visit frequency, duration, and associated costs for medical, psychological, and professional consultations.³⁰ CSI data will be collected at baseline and again at 12 months, with ITT analysis requiring baseline values to be duplicated for patients missing follow-up data. Visit counts for different service categories will be analyzed through linear models, with treatment status as the primary predictor. Mean visit duration per patient and visit type will be compared across the two groups using Welch's two-sample t-tests and linear regression models incorporating total visit count as a covariate. The impact of TCH on visit duration will be further assessed using analysis of variance (ANOVA) models to determine potential treatment group differences. Additionally, sub-analyses will be conducted to explore whether utilization patterns differ by age or baseline disease severity. Given the pragmatic design of the study, an emphasis will be placed on real-world applicability, ensuring that findings account for the variability seen in routine clinical settings.

Out-of-pocket (OOP) costs will be evaluated using a combination of t-tests, ANOVA, least squares regression, and random-effects gamma regression. Initial analyses will compare total OOP costs per visit and overall OOP costs between the two treatment groups using simple t-tests. Subsequently, multiple linear regression models will be used to assess the impact of TCH on total OOP costs while adjusting for relevant covariates such as treatment site, age, sex, baseline EASI score, and history of asthma. A sensitivity analysis will be performed using gamma regression models. Given that cost data often exhibit a skewed distribution, appropriate transformations or robust estimation methods will be applied where necessary to improve model fit and interpretability.³² Statistical significance for all analyses will be set at p<0.05, and all statistical computations will be conducted using standard statistical software such as R.

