9 STATISTICAL CONSIDERATIONS

9.1 SAMPLE SIZE DETERMINATION

We consider $\delta_U = \pm 6.5$ as the equivalence limit for our primary outcome, SA-EASI, which is half of a clinically significant difference and much more conservative than prior studies.¹¹ We computed sample size estimates for equivalency comparison of means for the primary endpoint and secondary endpoints from Aim 1 and Aim 2 using one-sided $\alpha = 0.05$ and 80% power (PASS version 14). 272 patients randomized are sufficient to determine equivalency with 80% power for the primary endpoint of EASI given the range of SD (15-20), with anticipated 15% attrition. This N is larger than that required for any

of the other outcomes.²³⁻²⁵ Thus, enrolling 300 patients provides adequate power to evaluate primary and all secondary outcomes and accounts for attrition.

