9.3 STATISTICAL ANALYSES

9.3.1 GENERAL APPROACH

For this pragmatic, randomized trial, we will compare patients randomized to the online, team-based connected health (TCH) versus patients receiving in-person care across one year. The overall analytical strategy is to use linear mixed or generalized estimating equations, depending on the outcome variable, to account for repeated measures within patients. Random effects for patients will be included in the model so that the estimates of any patient-level variables will be appropriately calculated. Additionally, we will adjust *a priori* for the randomization stratification factors site and age group (<18 years, and 18+ years) in all models. While we do not anticipate a site-level main effect, random effects for site will be included in the model in case there are factors common to patients within a site that affect the outcome.

For comparison of AD disease severity (Aim 1) and quality of life (Aim 2), we will test an equivalence hypothesis between the interventions using longitudinal linear mixed effects modeling; this allows for the estimation of intra-individual variance. Using this same technique, we will test the hypothesis of improved access to specialist care (Aim 2) and cost-saving (Aim 3) with the TCH model compared to the in- person model.

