9.3.2 ANALYSIS OF THE PRIMARY EFFICAY ENDPOINTS

The primary endpoint of the study is the mean improvement from baseline in EASI versus the follow-up visits (months 3-12). The comparison of improvement in EASI will incorporate all available post-intervention follow-up visits. Our primary goal will be to compare the mean difference in improvement between groups to examine if they are equivalent.

We will use an intent-to-treat (ITT) approach to evaluate equivalency of changes between the two arms across 12 months for AD-disease-severity and quality-of-life endpoints using longitudinal linear mixed modeling. This modeling allows us to account for intra-individual variability and the possibility of different numbers of follow-up measurements inherent in this pragmatic research design. For these analyses, the null hypothesis is that there is a differential treatment effect between the groups: H_0 : $\mu I_{n-person} \neq \mu_{TCH}$. The alternate hypothesis is H_A : $\mu_{In-person} = \mu_{TCH}$, where μ represents the average change from baseline across the follow-up visits (3 months – 12 months).

For the primary comparison of baseline versus average of follow-up visits, a dummy-coded time variable will be coded with 0 = baseline and 1 for all follow-up visits, so that the estimate of the effect will indicate the difference between baseline and the average of follow-up visits. In addition, a group

variable will be added to the model (coded 0 for in-person and 1 for TCH) along with a group x time effect.

We consider $\delta_0 = \pm 6.5$ as the equivalence limit for the primary endpoint of EASI. This equivalence limit of 6.5 was selected for EASI because it represents the minimal clinically important difference in the AD literature.²⁸ It is also more conservative than equivalency limits of 12-20 from pilot studies.²⁹

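### The vIGA equivalence margin of 0.5 reads as score points, but the ordinal GEE assigned to vIGA has no stated link, effect measure or route to a difference in points

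*Combined protocol and SAP*

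**What the plan says.** Section 9.3.3 describes vIGA as ordinal, with five categories scored 0 to 4, and specifies the analysis in three sentences:

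- Model: "We will apply the same general modeling procedure using generalized estimating equations with the ordinal outcome of vIGA".
- Coding: "The reference category will be 0 = clear".
- Margin: "The equivalence margin for vIGA is 0.5, which is smaller than the minimal clinically important difference".

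No link function, effect measure or unit for the 0.5 is given, and no step turns a model estimate into a score difference. The next paragraph of the same section gives POEM the EASI method, so vIGA is set apart on purpose.

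The general sections point two ways on the model. The first paragraph of section 9.3.1 allows "linear mixed or generalized estimating equations, depending on the outcome variable". Its second paragraph says of Aims 1 and 2 that "we will test an equivalence hypothesis between the interventions using longitudinal linear mixed effects modeling". Section 9.3.2 (and section 9.2 in near-identical words) plans to evaluate "equivalency of changes between the two arms across 12 months for AD-disease-severity and quality-of-life endpoints using longitudinal linear mixed modeling".

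**The concern.** An equivalence conclusion compares a confidence interval with a margin, so the two must be on the same scale. An ordinal GEE of the usual kind estimates effects on a logit or probit scale, whereas the margin appears to be in score points. If 0.5 were set against the model's own coefficient, the trial would test a different limit from the one that was justified. How different would depend on the link and on where patients sit on the scale, neither of which is stated. If the reference-category wording means a baseline-category logit, no single coefficient exists to test. The choice would then be made with data in hand, for an Aim 1 endpoint that has its own equivalence claim.

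**Working it through.** **Step 1: the unit of 0.5.** The plan does not state it. Four places imply points:

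- Sections 1.1 and 3 define the endpoint as change in vIGA from baseline, averaged over 12 months.
- In section 9.3.2 the tested quantity "represents the average change from baseline across the follow-up visits".
- Section 9.3.3 justifies the margin against the minimal clinically important difference.
- Section 9.1 describes the sizing as "equivalency comparison of means for the primary endpoint and secondary endpoints from Aim 1 and Aim 2".

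No passage mentions odds or log-odds.

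**Step 2: what the named model yields.** Section 9.3.2 codes time as 0 (baseline) or 1 (any follow-up visit), with group and group-by-time terms. Carried over to vIGA:

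| Reading of the vIGA model | Group-by-time estimate | Comparable with 0.5 points? |
|---|---|---|
| Identity link on the 0-4 score | difference in mean change, points | yes |
| Cumulative logit or probit | one coefficient, link scale | no |
| Baseline-category logit, reference clear | 5 − 1 = 4 coefficients | no; no single test |

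**Step 3: what a coefficient of 0.5 is worth in points (illustration).** There is no plan figure to reproduce: the documents give no vIGA distribution, SD or link. All distributions below are assumptions. With the arms equal at baseline, a coefficient b moves each cumulative probability as

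new P(Y ≤ k) = F(F⁻¹(P(Y ≤ k)) − b), for k = 0 to 3,

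and the mean score is 4 minus the sum of the four cumulative probabilities.

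Worked case: 20% in each category, logit, b = 0.5. The cumulative probabilities 0.2, 0.4, 0.6, 0.8 (sum 2.000) become 0.132, 0.288, 0.476, 0.708 (sum 1.604). The mean rises by 2.000 − 1.604 = 0.396 points.

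Size of the shift in points for b = ±0.5:

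| Assumed shares, vIGA 0/1/2/3/4 | Logit | Probit |
|---|---|---|
| .20/.20/.20/.20/.20 | 0.396 | 0.648 |
| .10/.20/.30/.30/.10 | 0.309-0.318 | 0.524-0.544 |
| .20/.30/.30/.15/.05 | 0.302-0.313 | 0.502-0.544 |
| .45/.30/.15/.08/.02 | 0.251-0.290 | 0.403-0.522 |
| .70/.20/.07/.02/.01 | 0.146-0.194 | 0.239-0.385 |
| .01/.02/.07/.20/.70 | 0.146-0.194 | 0.239-0.385 |
| .02/.08/.20/.40/.30 | 0.252-0.275 | 0.415-0.495 |
| .02/.18/.60/.18/.02 | 0.181 | 0.331 |
| .30/.15/.10/.15/.30 | 0.450 | 0.718 |

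**Step 4: bounds.** Each of the four cumulative probabilities can move by at most F(0.25) − F(−0.25).

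- Logit: 4 × tanh(0.125) = 0.497 points, so below 0.5 for every distribution.
- Probit: 4 × 0.1974 = 0.790 points, so it may exceed 0.5. In the table it does so in both directions in four of nine cases, straddles 0.5 in one, and stays below in four.

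**Step 5: improvement over time.** The conversion applies at follow-up, so it moves as patients improve. Start from the uniform distribution and let controls improve by 1.36 points (a shift of −2 logits):

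- Logit: 0.396 falls to 0.207-0.269 points.
- Probit: 0.648 falls to 0.33-0.50 points, so no longer looser than 0.5.
- Probit with only a 0.5-point improvement: 0.58-0.66 points, still looser.

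**The case against.** The strongest reply is that the plan never says 0.5 will be compared with a raw coefficient. Section 9.3.3 carries over the EASI procedure, whose contrast is baseline against the average of follow-up, and a GEE with an identity link would deliver that contrast in points. This cannot be excluded, because no link is stated. But declaring the outcome ordinal and naming a reference category has no purpose under an identity link, so the wording argues against it. If that link was intended, one sentence settles the matter.

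A second reply is that the linear-mixed-model wording in sections 9.2, 9.3.1 and 9.3.2 already gives an estimate in points. It shows that such a route exists. However, section 9.3.1 also lets the model depend on the outcome, and section 9.3.3 is the specific text for vIGA. The general wording therefore conflicts with it rather than resolving it.

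A third reply, that the conversions rest wholly on assumed distributions, is correct. They show that the scale matters; they do not estimate what this trial would see.

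A reader might infer that arms more than 0.5 points apart are likely to be called equivalent. The documents do not support that. It needs a probit link that nobody has named, a widely spread follow-up distribution and little improvement; with the 1.36-point improvement tested, the probit limit was not looser.

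A reader might also infer a power shortfall for vIGA. Without a vIGA SD or effect measure in the documents, none can be shown.

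**Conclusion.** The concern holds as a scale mismatch between the named model and the stated margin, together with two models named for one endpoint. It rests on two readings of the text: that 0.5 is in points, which four places imply but none states, and that the GEE is not an identity-link model. On those readings the vIGA decision rule is undefined as written. If 0.5 were nevertheless applied to a cumulative-logit coefficient, the limit would be about 0.15-0.45 points over the assumed distributions and never above 0.497 with equal baselines. That is stricter than the limit justified, so arms that truly differ by less than 0.5 points could fail to be declared equivalent. Under a probit the direction is not fixed. Only this secondary endpoint is affected; the primary EASI analysis has its model and its margin on the same scale. The change should be made before the data are analysed.

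**What to change.** 1. In section 9.3.3, define the vIGA estimand as the between-arm difference in mean change in vIGA points (average of months 3-12 minus baseline). Declare equivalence if its 90% CI lies within ±0.5 points; the 90% level matches the one-sided alpha of 0.05 in section 9.1.
2. Estimate it from the same linear mixed model as EASI and POEM, or from a GEE with an identity link. Keep the ordinal GEE, with its link named, as a supportive analysis without a margin.
3. Alternatively, keep the ordinal GEE as the main analysis, name the link, and standardise its fitted probabilities to a difference in mean score, with a delta-method or patient-level bootstrap CI.
4. Align sections 9.2, 9.3.1 and 9.3.2 with the choice, by an exception or cross-reference for vIGA.

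A margin stated as an odds ratio would also be coherent, but it would need its own justification, because 0.5 is defended against the minimal clinically important difference.

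The cost is a few sentences of SAP text and, for item 3, one extra computing step. The downside of item 2 is that the five-category scale is treated as interval, which a margin in points already implies. No change to data collection is needed.

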7 STUDY INTERVENTION DISCONTINUATION AND PARTICIPANT DISCONTINUATION/WITHDRAWAL

7.1 DISCONTINUATION OF STUDY INTERVENTION

The criteria for discontinuing the online intervention include (1) the patient expresses desire to discontinue study intervention, (2) the provider expresses desire to discontinue patient from study intervention for any reason, which include AD exacerbation or adverse events that cannot be managed online *for the remainder of the study*. We will record the reasons for discontinuing the study intervention in detail via structured data capturing.

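### vIGA is assigned to GEE with no stated handling of missing visits, so its equivalence test can be biased if severity-related loss differs by arm

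*Combined protocol and SAP*

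**What the plan says.** - **vIGA model (9.3.3, Aim 1).** "We will apply the same general modeling procedure using generalized estimating equations with the ordinal outcome of vIGA". The section does not state the working correlation, link, weighting, imputation, missing-data assumption or any sensitivity analysis.
- **vIGA margin (9.3.3).** "The equivalence margin for vIGA is 0.5, which is smaller than the minimal clinically important difference". The text does not say whether 0.5 is in grade points or log-odds.
- **EASI and POEM (9.3.2, 9.3.3).** EASI uses a longitudinal linear mixed model, and POEM follows the EASI method.
- **General approach (9.3.1).** Mixed models or GEE are to be used depending on the outcome. The section then adds: "Random effects for patients will be included in the model so that the estimates of any patient-level variables will be appropriately calculated". It goes on to say that the Aim 1 equivalence hypotheses are tested by linear mixed models. vIGA is an Aim 1 endpoint.
- **Attrition (9.1).** The sample size is set "with anticipated 15% attrition", with no split by arm or cause.
- **Stopping the online intervention (7.1).** The provider may stop it for reasons "which include AD exacerbation or adverse events that cannot be managed online". No in-person counterpart is given.
- **After stopping (7.2).** Patients are encouraged to finish the study whatever their response, and Month 12 data are sought. Months 3-9 after stopping are not mentioned.
- **Missing-data rule.** The only explicit one is in the Aim 3 text of 9.3.3. It carries the baseline Cornell Services Index forward and does not apply to vIGA.

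**The concern.** Two things stand out.

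First, the vIGA model is not determined. A marginal GEE has no patient random effects and is not a linear mixed model, so 9.3.1 and 9.3.3 cannot both hold for vIGA.

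Second, if 9.3.3 governs, vIGA gets weaker protection against missing visits than the other two Aim 1 endpoints. A likelihood-based mixed model, correctly specified, remains valid when loss depends on severity already recorded (missing at random, MAR). Unweighted GEE in general does not.

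The direction matters in an equivalence trial. If TCH is truly worse and its sicker patients are the ones whose later visits are missing, the observed TCH mean looks better than it is. The arms are drawn together, and a claim of equivalence becomes easier to reach.

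**Working it through.** **The plan's own figure.** The documents give no vIGA-specific N, power or error rate. The stated 272 is for EASI and reproduces from the inputs in 9.1 (margin 6.5, SD 20, one-sided alpha 0.05, 80% power):

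- n per arm = 2[SD(z0.95 + z0.80)/margin]^2 = 2[20(1.645 + 0.842)/6.5]^2 = 117.1, rounded up to 118, so 236 in total.
- 236 x 1.15 = 271.4, rounded up to 272.

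Attrition therefore enters only as a flat 15% inflation, with no component for arm or severity. Whether this one-sided formula suits an equivalence test is a separate matter.

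**Simulation inputs from the documents.** 300 patients allocated 1:1 (150 per arm); baseline plus four follow-ups; a group-by-time term with time coded 0 at baseline and 1 afterwards (9.3.2); 15% attrition overall; margin 0.5; one-sided alpha 0.05, so equivalence means a 90% CI inside the margin.

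**Assumptions not in the documents.** vIGA SD about 1.05; within-patient correlation about 0.58 (0.6 for the ordinal model); monotone dropout depending on the last vIGA, with log-odds slope 1 per grade unless stated; true difference at the margin with TCH worse. Robust standard errors were used, with 2,000 to 3,000 runs per scenario.

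**False-equivalence rate (nominal 5%)**

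| Attrition, in-person/TCH | 0-4 score, independence | Cumulative logit, independence (margin 0.5 / 0.9 log-odds) | 0-4 score, independence, Month 12 recovered in half | 0-4 score, exchangeable, MNAR loss |
|---|---|---|---|---|
| No dropout | 5.1% | 4.2% / 4.5% | - | - |
| 15/15, same mechanism | 4.6% | 4.9% / 4.2% | 4.8% | 4.2% |
| 15/15, severity-driven in TCH only | 14.7% | 14.4% / 14.0% | 12.6% | 10.6% |
| 10/20, same slope | 9.5% | 10.2% / 8.6% | 9.4% | 7.4% |

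In this model, 0.5 log-odds is about 0.28 grade and 0.9 log-odds is about 0.52 grade. The last column has dropout depending on the current, unobserved vIGA (missing not at random, MNAR).

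**Exchangeable fit under MAR.** An exchangeable working correlation on the 0-4 score, whose point estimate is close to a random-intercept mixed model, gave 4.2-6.2% in every MAR case. The cumulative-logit model was run with independence only.

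**Hand check.** With the far limit many standard errors away, the rate is approximately Phi(-1.645 + |bias|/SE) when the bias is towards zero. For the cumulative logit at 0.5 log-odds:

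- TCH only: bias -0.098, SE 0.169. Phi(-1.645 + 0.580) = 14.3%, against 14.4% simulated.
- 10/20: bias -0.059, SE 0.172. Phi(-1.645 + 0.343) = 9.7%, against 10.2% simulated.

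**Range.** Repeat simulations with independence at slope 1 gave 10.8%, about 13% and 13.5% for TCH-only loss, and about 8% for 10/20. Same-mechanism loss gave about 3% and 3.5%. At slope 2 the 0-4 independence fit gave 24.6% (TCH only), 12.8% (10/20) and 3.2% (same mechanism). A 5/25 split at slope 1 gave 20.0%. The documents give no basis for choosing among these slopes or splits.

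**The case against.** The strongest reply is that the documents do not describe severity-related loss of vIGA data. Section 7.1 concerns stopping the online intervention, not leaving the study. Section 2.2.1 lets TCH patients seek in-person care, 5.4.2 collects outcomes quarterly for all participants, 7.2 encourages completion, 7.3 defines loss to follow-up identically in both arms, and the analysis is ITT. A reader might infer from 7.1 that patients who flare drop out of the TCH data. The documents do not say so. What stands is narrower: after the intervention stops, 7.2 promises only an attempt at Month 12, and Months 3-9 supply three of the four follow-ups averaged in the endpoint. Recovering Month 12 in half of those who stop reduces the inflation only modestly, to 12.6% and 9.4%.

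A reader might also infer that GEE with 15% attrition inflates the error by itself. It does not. Equal loss with the same mechanism leaves the rate at or below about 5%, and the choice of working correlation decides most of the rest. The plan names none, so it cannot be said to have chosen independence.

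The inflation is also confined to one edge of the null. With TCH-only loss at slope 1 and an independence fit, false equivalence was 2.3% when TCH was worse by 0.6, and 0.6% when TCH was better by 0.51. The bias behind the 10.8% result is about 0.05 grade, a tenth of the margin (0.05/0.5).

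Finally, a mixed model is no cure if an exacerbation between visits causes the loss. Under MNAR loss the mixed-model-type fit still reached 7.4-10.6% in the two moderate patterns, and 20.0% in an extreme 0/30 split. This stands, and the fix must allow for it.

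**Conclusion.** The concern holds in conditional form. The contradiction between 9.3.1 and 9.3.3 is plain on the page and needs no simulation. If GEE is used as written, with nothing done about missing visits, false equivalence on vIGA can reach about 8-15% instead of 5%. That requires all of the following: loss related to severity (slope 1 per grade assumed), loss differing by arm (TCH-only severity-driven loss, or 10%/20% attrition), an independence working correlation, and TCH truly worse by about the 0.5 margin read as grade points. With the same mechanism in both arms the rate is about 3-5%. With an exchangeable or mixed-model-type fit it is about 3-6% under MAR.

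Arm-different loss is a reasonable inference from the one-sided stopping rule and the silence on Months 3-9, but it is not a stated fact. vIGA is a secondary endpoint, and the primary EASI conclusion is not affected. The change should be made because it is cheap and the possible bias favours the result the trial hopes to show.

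**What to change.** 1. In 9.3.3, analyse vIGA with the same linear mixed model as EASI and POEM on the 0-4 score, which matches a margin of 0.5 grade. Alternatively, use an ordinal mixed model with a patient random effect.
2. If GEE is kept, weight it by the inverse probability of remaining observed, or apply it after multiple imputation from earlier severity. Name the link and working correlation, and do not rely on an unweighted independence fit.
3. State the missing-data assumption for vIGA and the scale of the 0.5 margin.
4. In 9.3.1, limit patient random effects to the mixed models, and make the Aim 1 sentence agree with 9.3.3.
5. Add an MNAR sensitivity analysis for vIGA, since neither a mixed model nor weighting on observed severity protects against loss driven by unobserved exacerbations.
6. In 7.2, say whether the quarterly outcome assessments continue through Months 3-9 after the online intervention stops.

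The cost of items 1 to 5 is SAP wording, a different model call and one sensitivity analysis, with no new data. Item 6 is a clarification, because 5.4.2 already collects outcomes quarterly for all participants. The small downside is that an ordinal mixed model gives patient-specific odds ratios, so the mean difference to compare with 0.5 grade must be derived from it. The linear mixed model avoids this.

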1.2 SCHEMA

1.3 SCHEDULE OF ACTIVITIES (SOA)

Procedures/Assessments	Month 0 / Baseline	Month 3	Month 6	Month 9	Month 12
	+ 28 days	-7 days, +21 days	-7 days, +21 days	-7 days, +21 days	7 days, +28 days
Informed Consent	Х				
Randomization	Х				
Patient or parent/legal guardian					
training on utilization of the	Х				
teledermatology platform					
Baseline Demographics and Medical	x				
History	~				
Atopic Dermatitis Severity Assessments		1	1	1	r
EASI	Х	Х	Х	Х	Х
vIGA	Х	Х	Х	Х	Х
POEM	Х	Х	Х	Х	Х
Quality of Life Assessments			•		
DLQI / CDLQI	Х	Х	Х	Х	Х
EQ-5D-5L / EQ-5D-Y	Х	Х	Х	Х	Х
Access to Care					
Access to Care (Baseline)	Х				
Access to Care (Follow-up)	х	Х	х	х	Х
Healthcare Costs Assessments					
Cornell Services Index	х				Х
Safety Assessments					
Adverse Event Collection Form	Х	Х	Х	Х	Х

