5.4.2 RETENTION PLAN

Prior to study initiation, we will conduct pre-trial retention training for the study staff. Prior to enrollment, the study staff will communicate with eligible patients regarding the importance of completing all outcome assessments. We will emphasize the importance of full participation during screening, enrollment, and throughout the trial.

It is important to note that, for online and in-person visits between the provider and patients, these visits occur at an individualized frequency based on medical necessity. However, the collection of outcome assessments (disease-severity, quality-of-life endpoints, and selected access-to-care measures) occurs at a quarterly basis for all participants.

All subjects will be reminded via email, text, or telephone to submit their quarterly outcome assessments beginning 7 days prior to the due date. If a subject fails to submit the quarterly outcome assessments within 2 days of the due date, the subject will be contacted using telephone and/or electronic methods to remind them to submit the assessments. The study staff will also discuss with the participant strategies to improve adherence with the study requirements. If the participant cannot be contacted after at least five attempts, a certified return receipt letter will be sent to encourage continuation in the trial.

If a participant fails to complete a quarterly assessment within 21 days of the due date, the study staff will make at least five attempts to contact (at least three telephone calls, two emails, and, if necessary, a certified return receipt letter to the participant's last known mailing address or local equivalent method). These contact attempts will be documented in the participant's study file.

If a participant wishes to withdraw from the study, the study coordinators will attempt to collect the Month 12 visit data as well as detailed data on the reasons for the discontinuation from the study. The study coordinators are encouraged to share their ideas and experiences to promote participant retention via regular communication during staff meetings.

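### Sections 9.3.1 and 9.3.3 name different models for access to care, and 9.3.3 does not say how the repeated quarterly follow-up data enter the regression

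*Combined protocol and SAP*

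**What the plan says.** Section 9.3.1 sets the general rule: "The overall analytical strategy is to use linear mixed or generalized estimating equations, depending on the outcome variable, to account for repeated measures within patients". For disease severity and quality of life it names "longitudinal linear mixed effects modeling; this allows for the estimation of intra-individual variance", and then continues: "Using this same technique, we will test the hypothesis of improved access to specialist care (Aim 2) and cost-saving (Aim 3"). It also states that "we will adjust *a priori* for the randomization stratification factors site and age group", and applies this to every model.

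Section 9.3.3 states that the access hypothesis is one of superiority and that the measures are transportation and the time an evaluation takes. Its whole method is one sentence: "Linear regression models will be used to test whether there is a difference between the groups".

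On data collection, the Schedule of Activities (1.3) has a row "Access to Care (Follow-up") marked at Months 0, 3, 6, 9 and 12, and a separate baseline access form at Month 0 only. Section 5.4.2 says that collection of "selected access-to-care measures) occurs at a quarterly basis for all participants".

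The endpoint lists in the synopsis (1.1) and in section 3 attach no time frame to access. The quality-of-life endpoints beside it are defined as changes from baseline averaged over 12 months.

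**The concern.** Two sections name different models for the same endpoint, and nothing in the documents reconciles them. The section specific to this endpoint drops the three things that the general section supplies: a way of handling several answers from one patient, the longitudinal time frame, and the adjustment for site and age group.

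Improved access is part of the overall study hypothesis in section 4.1. The measures are patient-reported, and section 6.2 acknowledges that patients and providers cannot be blinded. With the unit of analysis left open, the choice among visit rows, one visit or a patient average could be made after the data are seen. These choices do not give the same standard error, and one of them does not hold its nominal error rate.

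**Working it through.** The plan gives no sample size, power, standard error or within-patient correlation for access to care, so there is no figure of its own to reproduce. The check compares the analyses that the 9.3.3 sentence would allow.

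**Inputs**
- Post-baseline occasions per patient: m = 4 (Months 3, 6, 9 and 12, section 1.3).
- Significance level: 5%. The p<0.05 statement stands in the cost part of 9.3.3 and gives no sidedness; two-sided is assumed.
- Patients: 300 randomized 1:1 with 15% attrition (sections 5.4.1 and 9.1), so 300 × 0.85 / 2 = 127.5, about 128 per arm.
- Within-patient correlation ρ: not in the documents. Assumed 0.1 to 0.7, equal between all pairs of visits, with equal variance at each visit.

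**Reading A: four follow-up rows per patient pooled as independent, group effect tested.** The design effect is DE = 1 + (m − 1)ρ = 1 + 3ρ. The reported standard error is 1/√DE of the true one, and the true two-sided error is 2 × (1 − Φ(1.96/√DE)). For example, at ρ = 0.5, DE = 1 + 3 × 0.5 = 2.5, 1/√2.5 = 0.632, and 2 × (1 − Φ(1.240)) = 21.5%.

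| Assumed ρ | DE | Reported SE / true SE | SE too small by | True error of a 5% test |
|---|---|---|---|---|
| 0.1 | 1.3 | 0.877 | 12% | 8.6% |
| 0.3 | 1.9 | 0.725 | 27% | 15.5% |
| 0.5 | 2.5 | 0.632 | 37% | 21.5% |
| 0.7 | 3.1 | 0.568 | 43% | 26.6% |

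A simulation of 4,000 trials with 128 patients per arm and four complete visits gave 15.8%, 21.0% and 25.7% at ρ = 0.3, 0.5 and 0.7, in agreement with the formula.

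**Reading B: regression on one value per patient, the mean of the follow-up visits.** The same simulation gave an error of 4.4% to 5.0%. Nothing is understated.

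**Reading C: regression on a single visit.** The test is valid. Its standard error relative to that of the four-visit mean is 1/√((1 + 3ρ)/4):
- ρ = 0.3: 1/√0.475 = 1.45
- ρ = 0.5: 1/√0.625 = 1.26
- ρ = 0.7: 1/√0.775 = 1.14

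So the cost is lost precision.

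**Reading D: baseline and follow-up rows stacked, group-by-time effect tested by ordinary regression.** The reported standard error is 1/√(1 − ρ) times the true one: 1.20, 1.41 and 1.83 at ρ = 0.3, 0.5 and 0.7. Here it is too large, and the test is conservative.

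The four readings therefore run from an inflated error rate, through a valid test, to a conservative one. The text of 9.3.3 does not choose among them.

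**The case against.** The strongest defence is that 9.3.1 already governs. It names access to care, requires repeated measures to be accounted for, and requires site and age group in all models. On that view the sentence in 9.3.3 is loose shorthand. The documents contain no rule that the specific section overrides the general one, so it cannot be assumed that analysts would follow 9.3.3 alone. This is a fair reading, but it does not remove the conflict. Just before the access paragraph, 9.3.3 expressly extends the repeated-measures approach to DLQI/CDLQI and EQ-5D. Access is left out of that statement and given a method of its own.

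A reader might infer that the plan understates the standard errors for access to care. The documents do not support that. Section 9.3.3 gives no data layout, and understatement occurs only under reading A. A patient-level regression keeps the error near 5%, and reading D errs in the opposite direction. Since the endpoint has no time frame, a single-visit or summary analysis is also compatible with the text.

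Two further qualifications stand. Section 5.4.2 limits quarterly collection to selected access measures, and the content of the forms is not shown, so not every access item need be repeated. The correlation range is an assumption, and the figures for reading A take four complete visits per patient although 15% attrition is expected.

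**Conclusion.** The inconsistency stands: 9.3.1 assigns access to care to a longitudinal linear mixed model, 9.3.3 assigns it to linear regression, and neither the time frame nor the handling of the quarterly follow-up forms is stated. The textual conflict is certain. Its numerical effect is conditional: a standard error 12-43% too small and a true error of about 9-27% arise only if four follow-up rows per patient are treated as independent and the group effect is tested, for an assumed correlation of 0.1-0.7. Other permitted readings are valid or conservative.

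This should be corrected before analysis because it concerns a stated superiority hypothesis in an unblinded trial. It is a secondary endpoint.

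**What to change.** Define the access endpoint over Months 3-12 in the synopsis, section 3 and section 9.3.3, and list which access measures are collected quarterly. Replace the 9.3.3 sentence with the 9.3.1 model: a linear mixed model on all available follow-up values, with a patient random effect, arm as predictor, and age group and site handled as 9.3.1 specifies. Add the baseline value of the same access measure where it is collected; this covariate goes beyond what 9.3.1 now lists. The mixed model also suits patients with unequal numbers of visits, which is the reason section 9.3.2 gives for using it on EASI.

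Linear regression on one pre-specified per-patient summary, adjusted for age group and site, is an acceptable alternative, provided that 9.3.1 is amended to say the same. Either way, state whether the test is one- or two-sided. The cost is a wording change to the plan, with no new data and no change to the schedule.
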